### **Outcome Data Collection**

*Primary outcomes (hospitalizations and arrests).* Hospitalization data will be collected from three sources: the Georgia Department of Behavioral Health and Developmental Disabilities (DBHDD, the State's mental health agency), the CSU in Savannah, and the CSU in Brunswick. Because DBHDD operates all state psychiatric hospitals, they have complete admission and discharge data for the study timeframe. However, DBHDD only collected CSU data beginning in January 2017; as such, the two CSUs serving as referral sites will also provide admission and discharge data for the full study period.

Arrest data will be provided by the Georgia Crime Information Center (GCIC), within the Georgia Bureau of Investigation (the lead state law enforcement agency), in the form of the participants' record of arrests and prosecutions (RAP sheets). GCIC receives monthly arrest reports from >600 state and local law enforcement agencies; this information is stored in GCIC's crime database and is summarized in the RAP sheet. To test our arrest-related hypotheses, we will extract all arrests for the 12 months after enrollment. Arrest data will be available for all participants.

*Secondary outcomes (housing and recovery).* Data collection for the two secondary outcomes will be collected in-person, though retention is expected to be difficult based on the serious psychosocial impairment of the study sample and experience in the initial study. Two housing-related measures will be used. The *Housing Satisfaction Scale* (HSS) has 19 items covering choice, safety, privacy, and proximity. The *Housing Instability Index* (HII) is a sum of 10 items that ask participants about their housing situations over the past six months; the time frame was adapted to four months for this study to match the follow-up timepoints.

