### **Data Analyses**

Between-group comparisons will rely on intention-to-treat analyses. Analyses involving hospitalizations and arrests will be performed using both binomial and Poisson generalized linear models for binary outcomes and counts, respectively. Analyses of change in housing and recovery measures will be performed using linear mixed models on all available data at each timepoint. Time in months will be used as a continuous predictor (growth curves) with measures at baseline, 4-, 8-, and 12-months. For the primary outcome analysis (12-month endpoint) the model structure will include group (ODR vs. CM), time, and group-by-time interactions, with a random intercept for subject. For those measures that indicate significant 2-group differences, we will compare ODR against ICM specifically, to further define effects (post-hoc analyses). For count/duration of hospitalizations and number of arrests, we will do conditional tests (comparing only those with non-zero values) to reduce the effects of zero inflation and get meaningful effect sizes across groups.

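### The added tests of admissions, hospital days and arrests in non-zero participants are not randomized comparisons, are not marked as supportive, and no all-randomized estimate of days is named

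*Combined protocol and SAP*

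**What the plan says.** The Outcome Data Collection section makes hospitalizations and arrests the primary outcomes. The Data Analyses section then says three things that bear on them.

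- The principle: "Between-group comparisons will rely on intention-to-treat analyses".
- The models for hospitalizations and arrests: "binomial and Poisson generalized linear models for binary outcomes and counts, respectively".
- A further step at the end of the section. "For count/duration of hospitalizations and number of arrests", the plan states: "we will do conditional tests (comparing only those with non-zero values) to reduce the effects of zero inflation", and gives as a second purpose to "get meaningful effect sizes across groups".

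The comparison of ODR with intensive case management is labelled post hoc. The conditional tests carry no label. Duration of hospitalization appears only in the conditional sentence, where it is listed alongside count.

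**The concern.** Whether a participant has any admission or arrest is settled after randomization, and it is something ODR is meant to change. Restricting a between-arm comparison to those with an event therefore compares two subsets that randomization did not form. If ODR prevents some events, the ODR participants who remain in the comparison may differ in risk from the control participants who remain. The zeros are also the good outcome, so setting them aside sets aside part of the result.

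Two things follow. First, a reader could be shown a non-zero-only ratio as the effect of ODR beside a Poisson or binomial result that says something different, with no stated rule for which one carries the inference. Second, no all-randomized estimate of days is explicitly planned. The any-event result does not supply one, because the same difference in the proportion with any stay can go with different differences in mean days.

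**Working it through.** The plan states no event rates, sample size or power, so there is no figure of its own to reproduce. All rates and stay lengths below are assumptions chosen to show how the two estimates relate.

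**Identity.** For a count or number of days Y, E[Y] = P(Y>0) × E[Y | Y>0]. Taking ODR over CM:

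non-zero-only ratio = all-randomized mean ratio ÷ risk ratio for any event.

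The two ratios agree only if the proportion with any event is the same in both arms.

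**Days.** Assume that in CM 40% have no stay, 30% have 5 days and 30% have 20 days. The mean is 0.3×5 + 0.3×20 = 7.5 per person randomized, and 7.5/0.6 = 12.5 among those with a stay.

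| ODR prevents | Any stay, ODR (CM 60%) | ODR mean, all | All-randomized ratio | ODR mean, non-zero | Non-zero-only ratio |
|---|---|---|---|---|---|
| (a) one third of short and of long stays | 40% | 0.2×5 + 0.2×20 = 5.0 | 5.0/7.5 = 0.67 | 5.0/0.4 = 12.5 | 1.00 |
| (b) half of short, a quarter of long | 37.5% | 0.15×5 + 0.225×20 = 5.25 | 0.70 | 5.25/0.375 = 14.0 | 1.12 |
| (c) a quarter of short, half of long | 37.5% | 0.225×5 + 0.15×20 = 4.125 | 0.55 | 4.125/0.375 = 11.0 | 0.88 |

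Check on (b): risk ratio 0.375/0.6 = 0.625, and 0.70/0.625 = 1.12. Cases (b) and (c) have the same any-stay result, 60% vs 37.5%, but differ in days saved per person: 7.5 − 5.25 = 2.25 against 7.5 − 4.125 = 3.375. With short/long stays of 3/14, 5/20, 5/40 and 7/30 days, (a) stays at 0.67 becoming 1.00, (b) runs from 0.70–0.72 to 1.12–1.16, and (c) from 0.53–0.55 to 0.84–0.88.

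**Counts, one Poisson rate per arm.** The mean among those with an event is L/(1 − exp(−L)).

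- Rates 1.5 vs 1.0: 1.931 vs 1.582, so the non-zero-only ratio is 0.82 against a true 0.67 (any event 78% vs 63%).
- Rates 0.40 vs 0.25: non-zero-only 0.93 against a true 0.63 (any event 33% vs 22%).

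Over control rates from 0.3 to 2.0 per year, a true 0.50 becomes 0.93 to 0.68 and a true 0.70 becomes 0.96 to 0.80.

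**Counts, mixed risk.** Assume 70% of participants at 0.5 per year and 30% at 3 per year. The CM mean is 0.7×0.5 + 0.3×3 = 1.25, with any event in 56%.

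- A 30% cut in both groups: all-randomized 0.70, non-zero-only 0.83 (any event 47% in ODR).
- Cuts of 50% in the low-risk and 10% in the high-risk group: ODR mean 0.7×0.25 + 0.3×2.7 = 0.985, ratio 0.79, non-zero-only 1.02 (any event 43%).

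**Is a plain Poisson test adequate for counts?** In that mixed-risk control distribution the variance of the rates is 0.7×0.25 + 0.3×9 − 1.25² = 1.3125. The variance of the count is 1.25 + 1.3125 = 2.5625, and variance/mean is 2.05. A nominal two-sided 5% Poisson test then uses an effective cut-off of 1.96/√2.05 = 1.37, which gives a type I error of about 17%.

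**Precision of a day ratio in (a).** The squared coefficients of variation are 71.25/56.25 = 1.267 (CM) and 60/25 = 2.400 (ODR). The standard error of the log ratio is √(3.667/n) for n per arm. The 95% interval around 0.67 is 0.39–1.13, 0.46–0.97 or 0.49–0.91 for an assumed 50, 100 or 150 per arm.

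**The case against.** The strongest reply is that the plan is largely protected already. It states intention-to-treat and names binomial and Poisson models that can include everyone randomized. The conditional tests come last. Any event plus amount among those with events is a recognized two-part description, and the product of the two ratios recovers the overall effect. Days are whole numbers and could be run as a Poisson count. In each worked example above, the any-event comparison, and for counts the rate comparison, still points to benefit. Most of this stands. What it does not supply is a label that ranks the conditional tests below the all-randomized models, a statement that days go into the Poisson model, or the combined result.

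Several stronger readings are tempting, and the documents do not support them.

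- *The conditional tests are the only analysis, or the only source of effect sizes.* The binomial and Poisson models contradict this.
- *The conditional ratio removes all benefit from prevention.* It removes only the any-event factor. In the Poisson example 0.82 remains because repeat events fall, and in (c) 0.88 remains.
- *The tests will make ODR look harmful.* Ratios above 1 need particular patterns, such as prevention concentrated in short stays or lower-risk participants, or they come from longer stays or chance. The documents do not show which applies.
- *The tests have confirmatory standing.* The plan gives them no rank in either direction.
- *Days are a named primary measure.* The primary outcomes are given as hospitalizations and arrests, without naming duration.
- *The sentence "For the primary outcome analysis (12-month endpoint) the model structure will include group (ODR vs. CM), time, and group-by-time interactions" elevates the conditional tests.* It describes a mixed model and follows the growth-curve text. Which outcomes it covers is a separate question.

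**Conclusion.** The point holds in a limited form and should be fixed. The non-zero-only tests sit under an intention-to-treat statement and are meant to yield effect sizes, yet they select on a post-randomization part of the primary outcomes, and nothing marks them as supportive. For any event and for counts the weakness is one of ranking, because all-randomized models are already planned. For duration the gap is complete as written, subject to the possible but unstated reading of days as a Poisson count.

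The size depends on assumed inputs throughout. A one-third reduction in mean days can vanish entirely (0.67 to 1.00), and a one-third reduction in a Poisson count can shrink to less than a fifth (0.67 to 0.82). These figures illustrate the mechanism and do not estimate what happened in this trial.

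**What to change.** State that inference and effect sizes for number of admissions, hospital days and number of arrests come from all randomized participants in their assigned arm, zeros included. Then:

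- Any event: the binomial model already planned.
- Counts: the Poisson log-link model with robust (overdispersion-corrected) variance, or a negative binomial model. A plain Poisson test should not carry the inference, given the type I error shown above and the plan's own expectation of zero inflation.
- Days: name an all-randomized model, for example a log-link model with robust variance, or a two-part model that reports the combined mean ratio and the difference in mean days per person.
- Non-zero-only comparisons: keep them, labelled as descriptive and not as estimates of the ODR effect.

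This takes a few sentences and no new data. The Outcome Data Collection section says arrest data will exist for every participant, the state agency's hospital data are complete, and the two referral crisis units supply admissions and discharges for the whole period.

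There are two costs. Mean days with many zeros will have wide intervals, as the precision check shows. Timing also matters: enrollment was to start in December 2014 and take about three years, while the document is dated September 2022 and revised July 2024. The documents do not say whether outcomes had been seen by then; if they had, the change must be disclosed as made after the data.
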